## **6.6 DOSE MODIFICATION AND TOXICITY MANAGEMENT GUIDELINES**

Dose modification associated with AL101 is described below in [Table 6](#).

The causality assessment system proposed by the World Health Organization Collaborating Centre for International Drug Monitoring, the Uppsala Monitoring Center (WHO-UMC) will be used by the Investigator for assessing drug-related (certain, probable/likely, possible) non-hematological Grade 3 (except isolated Grade 3 electrolyte abnormality that are not associated with clinical signs or symptoms and are reversed with appropriate medical intervention within 48 hours) and hematological Grade 4 toxicities will lead to a 1 dose level reduction for AL101. For easily manageable Grade 1 or 2 toxicity, no dose reductions are required, but careful observation and treatment is required. Dose modification of intolerable Grade 2 toxicity will be evaluated on a case-by-case basis with the Sponsor. Re-escalation of the dose following a dose reduction is allowed only after discussion and approval of the Sponsor's Medical Monitor. Maximum AL101 treatment interruption allowed is 28 days; treatment interruption longer than 28 days will result in discontinuation of patient from the study. Additional treatment guidelines may be implemented by the Investigators, with agreement of the Sponsor/Medical Monitor, as needed to ensure patient safety.

 "The use of the WHO-UMC system for standardized case causality assessment" a communication by WHO-UMC in 2011; [https://www.who-umc.org/media/164200/who-umc-causality-assessment\\_new-logo.pdf](https://www.who-umc.org/media/164200/who-umc-causality-assessment_new-logo.pdf)

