**Table 6 Dose Modification Criteria for AL101**

Dose Modification Criteria for AL101 -Related Adverse Events	AL101 modification	
	Note: for any questions, please contact the Sponsor's Medical Monitor.	
	Cohort 1 (4 mg QW IV)	Cohort 2 (6 mg QW IV)
Grade 4 neutropenia lasting $\geq$ 7 days	Decrease by 1 dose level to 2.4 mg QW.	Decrease dose to 4 mg QW for first episode and to 2.4 mg QW for second episode
Grade 3 febrile neutropenia lasting $>$ 24 hours	Decrease by 1 dose level to 2.4 mg QW.	Decrease dose to 4 mg f QW or first episode and to 2.4 mg QW for second episode.
Grade 4 febrile neutropenia	Discontinue.	Discontinue.
Grade 4 thrombocytopenia or $\geq$ Grade 3 thrombocytopenia with significant bleeding	Decrease by 1 dose level to 2.4 mg QW.	Decrease dose to 4 mg QW for first episode and to 2.4 mg QW for second episode
$\geq$ Grade 3 CD4+ T-cell depletion (counts $<$ 200 cells/ $\mu$ L)	Interrupt AL101 until resolution to Grade 1, then resume at 1 dose level lower (i.e., 2.4 mg QW) . If treatment interruption is longer than 28 days, the patient will be discontinued from the study.	Interrupt AL101 until resolution to Grade 1, then resume at 4 mg QW dose level. For second episode, reduce dose to 2.4 mg QW.  If treatment interruption is longer than 28 days, the patient will be discontinued from the study.
Grade 1 diarrhea	No change in AL101 dose. Guidelines for the management of diarrhea: 
 
• Loperamide 4 mg at the first onset of diarrhea, then 2 mg every 2 hours around-the-clock until diarrhea free for at least 12 hours. Patients may take loperamide 4 mg every 4 hours during the night. These doses should not be used for more than 48 hours due to the risk of paralytic ileus.
 
• For patients that cannot tolerate loperamide or do not get adequate relief with maximum
 
	No change in AL101 dose. Guidelines for the management of diarrhea: 
 
• Loperamide 4 mg at the first onset of diarrhea, then 2 mg every 2 hours around-the-clock until diarrhea free for at least 12 hours. Patients may take loperamide 4 mg every 4 hours during the night. These doses should not be used for more than 48 hours due to the risk of paralytic ileus.
 
• For patients that cannot tolerate loperamide or do not get adequate relief with maximum doses, standard doses of LOMOTIL®
 

Confidential

 Document State: Effective (Controlled)  
 CONFIDENTIAL

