	
 
For patients that cannot tolerate loperamide or do not get adequate relief with maximum doses, standard doses of LOMOTIL® (diphenoxylate/atropine) may be added or used instead of loperamide.
 
Additional antidiarrheal measures, such as octreotide, may be used at the discretion of the investigator or treating physician
 
Treat with dexamethasone at a dose of 8 mg every Q8h for up to 5 days. If still no improvement in symptoms, the patient may continue with the dexamethasone or consider switching to budesonide 9 mg QD. Refer to Section 7.1.2 for additional instructions on premedication with steroids.
 
 
If the above measures have not worked, or patient has progressed to Grade 4, consult GI as necessary to evaluate for colitis.
 
Dose modifications for AL101:
 
Permanently discontinue AL101 (refer to Section 4.5 for early withdrawal of patients from therapy or assessment).
	
standard doses of LOMOTIL® (diphenoxylate/atropine) may be added or used instead of loperamide.
 
 
Additional antidiarrheal measures, such as octreotide, may be used at the discretion of the investigator or treating physician
 
Treat with dexamethasone at a dose of 8 mg Q8h for up to 5 days. If still no improvement in symptoms, the patient may continue with the dexamethasone or consider switching to budesonide 9 mg QD. Refer to Section 7.1.2 for additional instructions on premedication with steroids.
 
 
If the above measures have not worked, or patient has progressed to Grade 4, consult GI as necessary to evaluate for colitis.
 
Dose modifications for AL101:
 
Permanently discontinue AL101 (refer to Section 4.5 for early withdrawal of patients from therapy or assessment).

Diagnosed or suspected clinically significant gastrointestinal (GI) bleeding or unexplained drop in hemoglobin	
Interrupt AL101, perform appropriate diagnosis and treatment.
 
If GI bleeding is considered related to AL101 reduce 1 dose level to 2.4 mg QW.
	
Interrupt AL101, perform appropriate diagnosis and treatment.
 
If GI bleeding is considered related to AL101, Decrease to 4 mg QW for first episode and to 2.4 mg QW for second episode 1 dose level.

Confidential

 Document State: Effective (Controlled)  
 CONFIDENTIAL

Page 58 of 118

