Dose Modification Criteria for AL101 -Related Adverse Events	AL101 modification	
	Note: for any questions, please contact the Sponsor's Medical Monitor.	
	Cohort 1 (4 mg QW IV)	Cohort 2 (6 mg QW IV)
	
If colitis is suspected please refer to Section 8.4.2, Table 10 for management guidelines for colitis.
 
If treatment interruption is longer than 28 days, the patient will be discontinued from the study.
	
If colitis is suspected please refer to Section 8.4.2, Table 10 for management guidelines for colitis.
 
If treatment interruption is longer than 28 days, the patient will be discontinued from the study.

Grade 3 or 4 gastric hemorrhage	
Permanently discontinue AL101 (refer to Section 4.5 for early withdrawal of patients from therapy or assessment).
	
Permanently discontinue AL101 (refer to Section 4.5 for early withdrawal of patients from therapy or assessment).

QTcF > 500 msec confirmed by at least one repeat ECG and at least 50 msec above baseline	
Interrupt if needed to optimize electrolyte management. If persists after electrolyte optimization (including dose modification of AL101 if necessary), discontinue.
 
If treatment interruption is longer than 28 days, the patient will be discontinued from the study.
	
Interrupt if needed to optimize electrolyte management. If persists after electrolyte optimization (including dose modification of AL101 if necessary), discontinue.
 
If treatment interruption is longer than 28 days, the patient will be discontinued from the study.

AST or ALT > 5 times the institutional ULN	
Interrupt AL101 until resolution to <math>\leq</math> Grade 1 and then resume at 1 dose level lower (i.e., 2.4 mg QW). Refer to Section 8.4.1 for hepatic function abnormalities and Section 8.4.5 for drug-induced liver toxicity management.
 
If treatment interruption is longer than 28 days, the patient will be discontinued from the study.
	
Interrupt AL101 until resolution to <math>\leq</math> Grade 1 and then decrease dose to 4 mg QW for first episode and to 2.4 mg QW for second episode.
 
Refer to Section 8.4.1 for hepatic function abnormalities and Section 8.4.5 for drug-induced liver toxicity management.
 
If treatment interruption is longer than 28 days, the patient will be discontinued from the study.

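### The Section 6.6 summary sentence reduces the dose for three events where Tables 6 and 10 stop treatment, and Table 6 gives two answers for some Grade 4 GI bleeding

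*Protocol*

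**What the plan says.** Section 6.6 of the protocol opens by pointing to Table 6 for dose modification. It then states a rule of its own. The sentence is grammatically broken, but its readable content is that drug-related non-hematological Grade 3 "and hematological Grade 4 toxicities will lead to a 1 dose level reduction for AL101". One exception is given, for isolated Grade 3 electrolyte abnormalities without symptoms that are corrected within 48 hours. Nothing says which prevails if the sentence and the table differ.

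The tables contain these rows:

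- Table 6, "Grade 4 febrile neutropenia": discontinue, in both cohorts.
- Table 6, "Grade 3 or 4 gastric hemorrhage": permanently discontinue, in both cohorts.
- Table 10 (Section 8.4.2), Grade 3-4 colitis: permanently discontinue.
- Table 6, "Diagnosed or suspected clinically significant gastrointestinal (GI) bleeding or unexplained drop in hemoglobin": interrupt and investigate. For Cohort 1 it adds "If GI bleeding is considered related to AL101 reduce 1 dose level to 2.4 mg QW". For Cohort 2 a related bleed goes to 4 mg at the first episode and 2.4 mg at the second. The row carries no grade.
- Table 6, last row: permanent discontinuation for Grade 4 non-hematologic adverse events, including Grade 4 non-hematologic laboratory abnormalities lasting more than 72 hours.

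The header of Table 6 adds "Note: for any questions, please contact the Sponsor's Medical Monitor".

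**The concern.** A dose rule should give one answer for one event. Here a reader of the Section 6.6 sentence lowers the dose and continues, while a reader of the tables stops. The events include Grade 4 toxicity, which Table 8 defines in general as life-threatening. A similar split arises inside Table 6 for some GI bleeding, and there a pointer to the table cannot settle it.

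What is at stake is consistent handling of patients across sites and, later, a clear standard for what counts as a dosing deviation. SAP Section 7.3.2 has major deviations defined before database lock, and SAP Section 7.2 removes patients with major deviations from the Per-Protocol set. That set is used for a sensitivity analysis of ORR (SAP Section 7.5.2).

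**Working it through.** No sample size, power or error rate is involved, so the check is a comparison of rules.

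**Step 1: the Section 6.6 sentence against the tables.**

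| Event (drug-related) | Section 6.6 sentence | Table |
|---|---|---|
| Grade 4 febrile neutropenia | reduce one level (hematological Grade 4) | Table 6: discontinue, both cohorts |
| Grade 3 gastric hemorrhage | reduce one level (non-hematological Grade 3) | Table 6: permanently discontinue, both cohorts |
| Grade 3 colitis | reduce one level (non-hematological Grade 3) | Table 10: permanently discontinue |

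That is one event from the hematological half of the sentence and two from the non-hematological half: 1 + 2 = 3. The electrolyte exception touches none of them. The documents do not define hematological. Table 6 lists febrile neutropenia between neutropenia and thrombocytopenia, so classing it as hematological is the natural reading.

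For colitis the cross-references do not help. Table 6 has no colitis row. It mentions Table 10 only within the GI-bleeding row, and Section 8.4 sends the reader back to Section 6.6 for dose modification of events of special interest.

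**Step 2: overlap within Table 6.** Take a Grade 4 GI bleed related to AL101.

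- If the source is gastric, the gastric-hemorrhage row says stop.
- If it is colitis, Table 10 says stop.
- Otherwise the GI-bleeding row applies, because it has no grade limit, and leads to interruption and then reduction. The Grade 4 non-hematologic row applies too, and stops treatment.

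Other rows are fenced off from one another. Diarrhea is split by grade, and the Grade 3 catch-all is confined to events not listed elsewhere. The Grade 4 row has no such limit and no statement that it overrides the others.

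The 72-hour condition can be read two ways. If it attaches only to laboratory abnormalities, every such Grade 4 bleed meets both rows. If it attaches to adverse events as well, only bleeds lasting more than 72 hours do. The overlap survives either reading but is narrower under the second.

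**Step 3: result.** Three events where sentence and table disagree on stopping, and one overlap inside Table 6.

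**The case against.** The strongest reply is that Section 6.6 names Table 6 as the place where dose modification is described. A site would then follow a row naming the exact event in preference to a garbled summary. For febrile neutropenia and gastric hemorrhage that is probably what happens. The GI-bleeding and Grade 4 rows can also be read together: manage the bleed under one, and if it is Grade 4, stop under the other. That is a sensible reading, and the fix adopts it, but the table does not say so.

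The controls are real. Sites are told to ask the Medical Monitor. Section 4.5 requires interruption for related serious reactions, and restart needs Medical Monitor approval after resolution to baseline. A life-threatening event is serious under Section 8.2. A reader might therefore infer that a site may re-dose after a life-threatening event on its own reading of Section 6.6; Section 4.5 does not allow that. For the Grade 3 events, this control applies only when the event is also serious. None of these provisions says which dose rule applies.

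Two further inferences are tempting and not supported:

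- That "AST or ALT > 5 times the institutional ULN" is a second overlap with the Grade 4 stop row. This needs Grade 4 to lie above 5 times ULN, a cut-off the documents do not give. It also depends on the liver-injury algorithm in Figure 2, which is not shown. Hy's law cases have their own stop row. It is a point to check and is not counted.
- That the row beginning "Grade 4 neutropenia lasting", which has a 7-day threshold, contradicts the sentence for shorter episodes. The sentence calls for a reduction and the table implies none, but neither stops treatment. It is a clarification only.

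Finally, dosing may be over. SAP Section 4 places its update between dry-run and database lock, SAP Section 6.3.2 describes enrollment in the past tense, and SAP Table 7 censors at July 31, 2022. An amendment might then come too late to guide dosing, which leaves the deviation question.

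**Conclusion.** Wrong as written; minor severity. The Section 6.6 sentence gives the opposite instruction to the tables for three events. Separately, Table 6 gives two instructions for related Grade 4 GI bleeding that is neither gastric nor colitis, limited to bleeds over 72 hours if that condition covers adverse events. The first part rests on treating febrile neutropenia as hematological and on the plain words of the rows.

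Practical risk is limited by the pointer to Table 6, the Medical Monitor contact and Section 4.5. The documents do not say how many patients had these events. A reader might infer that the trial's main result is in doubt. It is not: sample size and the primary ORR analysis do not depend on these rules. The only analysis link is through major deviations and the Per-Protocol set.

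**What to change.** Add to Section 6.6 that Table 6, and Table 10 for colitis, govern over the summary sentence. An exception for febrile neutropenia alone would leave the two Grade 3 conflicts standing. Table 10 has to be named because, with no colitis row in Table 6, Grade 3 colitis could be placed in the Grade 3 catch-all row, which does not stop treatment.

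Add to Table 6 that the Grade 4 non-hematologic stop row takes precedence over the GI-bleeding row. Keep this wording specific to that row: Section 7.1.1 provides for possible re-treatment after Grade 4 infusion reactions, and a blanket override would collide with it. The sponsor's medical team should confirm the rule, check whether the same precedence should apply to the AST/ALT row, and say whether Grade 4 neutropenia under 7 days needs a reduction.

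If dosing has ended, list the patients with these events and decide before database lock which rule counts when major deviations are defined for the Per-Protocol set.

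The cost is a few sentences in an amendment or clarification letter or, after dosing, one listing and one recorded decision. Sample size and the primary ORR analysis do not change.

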Confidential

 Document State: Effective (Controlled)  
 CONFIDENTIAL

Page 56 of 118

Dose Modification Criteria for AL101 -Related Adverse Events	AL101 modification	
	Note: for any questions, please contact the Sponsor's Medical Monitor.	
	Cohort 1 (4 mg QW IV)	Cohort 2 (6 mg QW IV)
	
Interrupt AL101 until resolution to <math>\leq</math> Grade 1 (refer to Section 6.6.2 and above for management guidelines for diarrhea).
 
Decrease AL101 dose to 2.4 mg QW.
 
If the diarrhea does not resolve to Grade 1 by 14 days, the patient will be discontinued from AL101 (refer to Section 4.5 for early withdrawal of patients from therapy or assessment).
 
If treatment interruption is longer than 28 days, the patient will be discontinued from AL101 (refer to Section 4.5 for early withdrawal of patients from therapy or assessment).
	
Interrupt AL101 until resolution to <math>\leq</math> Grade 1 (refer to Section 7.1.2 and above for management guidelines for diarrhea).
 
Change dose regimen to 6 mg 2 weeks on / 1 week off for the first episode.
 
Decrease AL101 dose to 4 mg QW for second episode and to 2.4 mg QW for third episode
 
If the diarrhea does not resolve to Grade 1 by 14 days, the patient will be discontinued from AL101 (refer to Section 4.5 for early withdrawal of patients from therapy or assessment).
 
If treatment interruption is longer than 28 days, the patient will be discontinued from AL101 (refer to Section 4.5 for early withdrawal of patients from therapy or assessment).

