Any other AL101-related Grade 3 nonhematologic adverse event except electrolyte abnormalities that may be managed with supplements	Interrupt AL101 until resolution to $\leq$ Grade 1 and then resume at 1 dose level lower (i.e., 2.4 mg QW). If treatment interruption is longer than 28 days, the patient will be discontinued from the study (refer to Section 4.5 for early withdrawal of patients from therapy or assessment).	Interrupt AL101 until resolution to $\leq$ Grade 1 and then change dose regimen to 6 mg 2 weeks on / 1 week off for the first episode. Decrease dose to 4 mg QW for second episode and to 2.4 mg QW for third episode. If treatment interruption is longer than 28 days, the patient will be discontinued from the study (refer to Section 4.5 for early withdrawal of patients from therapy or assessment).

Confidential

 Document State: Effective (Controlled)  
 CONFIDENTIAL

Page 60 of 118

Dose Modification Criteria for AL101 -Related Adverse Events	AL101 modification	
	Note: for any questions, please contact the Sponsor's Medical Monitor.	
	Cohort 1 (4 mg QW IV)	Cohort 2 (6 mg QW IV)
Grade 4 non-hematologic AEs including Grade 4 non-hematologic lab abnormalities lasting > 72 hours	Permanently discontinue from IP (refer to Section 4.5 for early withdrawal of patients from therapy or assessment ).	Permanently discontinue from IP (refer to Section 4.5 for early withdrawal of patients from therapy or assessment ).

Confidential

 Document State: Effective (Controlled)  
 CONFIDENTIAL

Page 61 of 118

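### For Cohort 2, Protocol Section 6.6 and Table 6 give different instructions after a first Grade 3 diarrhea or other catch-all Grade 3 non-hematologic event, and neither says which prevails

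*Protocol*

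**What the plan says.** Protocol Section 6.6 opens with a pointer to Table 6: "Dose modification associated with AL101 is described below in". Its next paragraph gives a general rule in one long, grammatically broken sentence. The first half names the events, "assessing drug-related (certain, probable/likely, possible) non-hematological Grade 3", with a parenthesis exempting isolated Grade 3 electrolyte abnormalities that cause no signs or symptoms and are reversed within 48 hours. The second half adds the blood toxicities and the action: "hematological Grade 4 toxicities will lead to a 1 dose level reduction for AL101". The sentence must be read whole, because its closing words alone name only the hematological events. It mentions no cohort and no episode number.

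Table 6 has separate columns for the two cohorts. For Grade 3 diarrhea in Cohort 2, after interruption and recovery, it says: "Change dose regimen to 6 mg 2 weeks on / 1 week off for the first episode". It continues: "Decrease AL101 dose to 4 mg QW for second episode and to 2.4 mg QW for third episode". The catch-all row covers "Any other AL101-related Grade 3 nonhematologic adverse event except electrolyte abnormalities that may be managed with supplements"; after interruption and recovery, its Cohort 2 entry says: "then change dose regimen to 6 mg 2 weeks on / 1 week off for the first episode". The second and third episodes then follow the same steps as for diarrhea.

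SAP Section 7.8.1 will report how many patients had a planned reduction from 6 to 4 mg or from 4 to 2.4 mg. It names no category for a change of schedule at an unchanged dose.

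**The concern.** An investigator with a Cohort 2 patient who has a first drug-related Grade 3 diarrhea finds two instructions in the same section. Both are worded as requirements, and they cannot both be followed. The catch-all row extends the conflict to every Grade 3 non-hematologic event that has no row of its own.

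This matters most at 6 mg. Protocol Section 1.4.1 reports that the previous developer recommended 4 mg as the maximum tolerated weekly dose in solid tumors, with dose-limiting toxicities at 6 mg and 8.4 mg. The same section relies on the toxicity management guidelines to justify opening Cohort 2. Those guidelines should give one answer for one event.

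There is also an analysis consequence. The same first event enters the SAP table as a 6-to-4 mg reduction if the site followed the text, and does not if it followed Table 6.

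**Working it through.** No power or alpha figure is involved. The check sets the passages side by side and then does simple dose arithmetic.

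**Step 1. Could the schedule change itself be the one-level reduction?** No. Table 6 uses dose level for steps in mg (in Cohort 1, one level down from 4 mg QW is 2.4 mg QW). The Amendment 3 summary describes the two-on/one-off regimen as a step that comes before dose reduction.

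**Step 2. Which Cohort 2 rows conflict?** The Section 6.6 sentence gives one level down for every drug-related Grade 3 non-hematologic event outside its electrolyte exception.

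| Event, first episode, Cohort 2 | Table 6 or Table 10 | Against the 6.6 sentence |
|---|---|---|
| Grade 3 diarrhea | interrupt, then 6 mg, two weeks on / one off | conflicts |
| Any other Grade 3 non-hematologic event (catch-all) | interrupt, then 6 mg, two weeks on / one off | conflicts |
| AST or ALT > 5 × ULN | interrupt, then 4 mg QW | agrees |
| Persistent Grade 3 triglycerides | interrupt, then 4 mg QW | agrees |
| AL101-related GI bleeding (row not graded) | interrupt, then 4 mg QW | agrees |
| Grade 3 or 4 gastric hemorrhage | permanent discontinuation | differs |
| Grade 3-4 colitis (Table 10) | permanent discontinuation | differs |
| Grade 3 or higher infusion reaction | interruption; no level reduction stated in the row | differs |

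In Cohort 1 the diarrhea and catch-all rows go to 2.4 mg QW, in line with the text. The two rows that keep the full mg dose are a Cohort 2 matter only.

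**Step 3. Dose after a first event.** Inputs: Table 6 orders the Cohort 2 steps as 6, 4 and 2.4 mg, so one level below 6 mg is taken as 4 mg.

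- Starting regimen: 6 mg × 4 = 24 mg per 28 days.
- Text rule: 4 mg × 4 = 16 mg per 28 days, or 4 mg/week.
- Table rule: 2 × 6 mg = 12 mg per 3 weeks; 12 / 3 = 4 mg/week, or 16 mg per 28 days on average.
- Both are 16 / 24 = two thirds of the starting intensity.
- Dose per infusion: 6 / 4 = 1.5, so 50% higher under the table.

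**Step 4. Dose after a second event.** Table rule: 4 mg QW, or 4 mg/week. If the text rule is applied again, one level below 4 mg is 2.4 mg QW, or 2.4 mg/week; 2.4 / 4 = 0.6, so 40% lower than under the table. The equality of average dose therefore holds only until a second event.

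**Step 5. How many patients?** The documents give no event rate at 6 mg in this study. Two figures bracket an illustration for Grade 3 diarrhea among 42 patients:

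- 3.4% Grade 3 diarrhea reported in this study before Cohort 2 (Section 1.3.2): 42 × 0.034 = 1.4 patients.
- 8/43 = 18.6% treatment-related Grade 3 or higher diarrhea at 4 mg QW in study CA216001 (Section 1.4.1): 42 × 8/43 = 7.8 patients.

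The second figure may include Grade 4 events, for which Table 6 requires discontinuation. Neither figure counts catch-all events.

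**The case against.** The best defence is that Table 6 governs. Section 6.6 points to it in its first line, and it is specific by cohort, event and episode where the prose is general. The Amendment 3 summary shows that the new regimen was deliberate for a first Grade 2 or 3 diarrhea. Section 6.6.2 allows for reduction of dose, frequency or both, and the table header sends questions to the Medical Monitor.

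This makes Table 6 a reasonable reading, but it does not remove the contradiction. No precedence is stated, and the general sentence is mandatory. The amendment summary does not mention the catch-all row. Section 6.6.2 offers options to consider, which amounts to a third formulation. An investigator who finds either passage clear has no reason to ask the Medical Monitor.

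Three stronger inferences are not supported:

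- That every first Grade 3 non-hematologic event in Cohort 2 is left at 6 mg. Step 2 shows rows that go to 4 mg QW, and others that lead to discontinuation or interruption.
- That exposure and tolerability at 6 mg cannot be interpreted. Average weekly dose is equal after a first event, and SAP Section 7.8.1 also summarizes infusions attempted, total mg received, cycles initiated, and administrations not given as planned with reasons.
- That sites did manage patients differently. The wording makes this possible, but the documents do not show that it happened.

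**Conclusion.** The contradiction is real and stands in current text. It covers the first episode of Grade 3 diarrhea and of any catch-all Grade 3 non-hematologic event, in a cohort of up to 42 patients. The two rules share an average of 4 mg/week after that event. They differ in dose per infusion (6 versus 4 mg), in schedule, in the next step-down (4 versus 2.4 mg QW), and in whether the event counts as a 6-to-4 mg reduction. Cumulative exposure remains recoverable; the reduction count and any reading of per-infusion tolerability depend on which rule was followed.

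This rests on taking 4 mg as one level below 6 mg, as in Table 6, and on applying the text rule afresh at a second event. The number of patients affected at 6 mg is unknown. The point should be corrected, but it does not undermine the primary analysis. No view is taken on which rule is right.

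**What to change.** The sponsor should reconcile the general sentence in Section 6.6 with the Cohort 2 entries of Table 6 for Grade 3 diarrhea and for the catch-all row. The same edit should cover the entries where a Grade 3 event leads to discontinuation (gastric hemorrhage; Grade 3-4 colitis in Table 10) or to interruption (infusion reactions), so that one rule applies to each event. It should also align the electrolyte exception, which the text ties to absence of symptoms and reversal within 48 hours and Table 6 ties to management with supplements. The cost is a wording change or a clarification letter.

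Dosing may already be complete: SAP Section 4 places the update between dry run and database lock, Section 6.3.2 describes enrollment in the past tense, and Table 7 fixes a censoring date of July 31, 2022. In that case the SAP or study report should state which rule sites applied, and Section 7.8.1 should tabulate changes to the two-on/one-off schedule separately from mg-level reductions. The cost is a sentence and a table row, assuming that schedule changes were recorded or can be derived from infusion dates and doses.
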